The change from baseline IGA score will be analyzed using a mixed model for repeated measures (MMRM). The MMRM model will include change from baseline in IGA score as the dependent variable, treatment, study visit, treatment-by-visit interaction, and age group as fixed effects, subject as a random effect, and baseline IGA score as a covariate. All post-baseline study visits will be included in the model; however, the primary comparison will be between the active trifarotene cream HE1 groups and vehicle at Day 90. An unstructured covariance matrix will be used to model the within-subject errors. The Kenward-Roger approximation will be used to estimate degrees of freedom. In case of convergence issues, other covariance structures will be explored including autoregressive (AR(1)), compound symmetry (CS), and variance components (VC) with each model fit to find the covariance structure with the best fit. The fit statistics will be compared for all covariance structures; the structure with the smallest Akaike information criterion will be retained as the preferred model and noted in the resulting table. For the OLE period, the model will not include treatment or treatment-by-visit interaction since all subjects receive the same treatment in the OLE.

The least squares (LS) mean change from baseline will be presented along with the associated 95% CI within each treatment group. The overall *P* value of the model will be presented to test

the null hypothesis that the change from baseline to subsequent study visit is 0 with a 2-sided alternative considering a difference in either direction.

In comparing treatments (active trifarotene cream HE1 groups minus vehicle), LS mean differences in change from baseline will be presented along with associated 95% CIs and *P* values. The null hypothesis that the difference in change from baseline in active trifarotene cream HE1 groups minus control vehicle is 0 with a 2-sided alternative considering a difference in either direction. Even if a difference from vehicle is observed, as described above, successful treatment is defined as clear/almost clear overall (IGA scores of 0 or 1) and at least a 2-grade change from baseline.

The observed value and change from baseline in IGA score will also be summarized descriptively by study visit and treatment group using descriptive statistics in addition to the above noted models for the Double-blind Period and OLE. Categorical IGA scores will also be presented.

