8.2. Secondary Efficacy Analyses

8.2.1. Visual Index for Ichthyosis Severity (VIIS)

The investigator will rate the subject's condition using the 5-point VIIS for each body area (chest/abdomen, back, legs, and arms) and an overall score at all clinic visits. The scoring is as follows in [Table 5](#).

Table 5: VIIS Scoring Definitions

Score	Definition
0	Normal skin; no perceptible scale, or smoothening
1	Areas of normal skin intermixed with areas showing smoothening (diminished fine skin markings; shininess; waxiness) or small scales (visible separated/fractured stratum corneum)
2	Confluent smoothening (diminished fine skin markings; shininess; waxiness) or small scales (visible separated/fractured stratum corneum)
3	Confluent scales (visibly separated/fractured stratum corneum) including some large (>1cm), thick scales
4	Confluent, primarily large, thick scales

The change from baseline VIIS score will be analyzed using an MMRM. The MMRM model will include change from baseline in VIIS score as the dependent variable, treatment, study visit, treatment-by-visit interaction, and age group as fixed effects, subject as a random effect, and baseline VIIS score as a covariate. All post-baseline study visits will be included in the model; however, the primary comparison will be between the active trifarotene cream HE1 groups and vehicle at Day 90. An unstructured covariance matrix will be used to model the within-subject errors. The Kenward-Roger approximation will be used to estimate degrees of freedom. In case of convergence issues, other covariance structures will be explored including AR(1), CS, and VC with each model fit to find the covariance structure with the best fit. The fit statistics will be compared for all covariance structures; the structure with the smallest Akaike information criterion will be retained as the preferred model and noted in the resulting table. For the OLE period, the model will not include treatment or treatment-by-visit interaction since all subjects receive the same treatment in the OLE.

The LS mean change from baseline will be presented along with the associated 95% CI within each treatment group. The overall *P* value of the model will be presented to test the null hypothesis that the change from baseline to subsequent study visit is 0 with a 2-sided alternative considering a difference in either direction.

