8.2.2. Individual Score for Roughness

The amount of roughness of the skin overall will be measured on a 5-point scale at all clinic visits. The scoring is as follows in [Table 6](#).

Table 6: Roughness Scoring Definitions

Score	Definition
0	Clear: Smooth skin
1	Almost clear: Hardly palpable roughness
2	Mild: Mild roughness on palpation (fine sand paper-like)
3	Moderate: Moderate, coarse roughness (coarse sand paper-like)
4	Severe: Very coarse skin (broken cornflakes-like)

The change from baseline individual score for roughness will be analyzed using an MMRM. The MMRM model will include change from baseline in individual score for roughness as the dependent variable, treatment, study visit, treatment-by-visit interaction, and age group as fixed effects, subject as a random effect, and baseline individual score for roughness as a covariate. All post-baseline study visits will be included in the model; however, the primary comparison will be between the active trifarotene cream HE1 groups and vehicle at Day 90. An unstructured covariance matrix will be used to model the within-subject errors. The Kenward-Roger approximation will be used to estimate degrees of freedom. In case of convergence issues, other covariance structures will be explored including AR(1), CS, and VC with each model fit to find the covariance structure with the best fit. The fit statistics will be compared for all covariance structures; the structure with the smallest Akaike information criterion will be retained as the preferred model and noted in the resulting table. For the OLE period, the model will not include treatment or treatment-by-visit interaction since all subjects receive the same treatment in the OLE.

The LS mean change from baseline will be presented along with the associated 95% CI within each treatment group. The overall *P* value of the model will be presented to test the null hypothesis that the change from baseline to subsequent study visit is 0 with a 2-sided alternative considering a difference in either direction.

In comparing treatments (active trifarotene cream HE1 groups minus vehicle), LS mean differences in change from baseline will be presented along with associated 95% CIs and *P* values. The null hypothesis that the difference in change from baseline in active trifarotene cream HE1 groups minus control vehicle is 0 with a 2-sided alternative considering a difference in either direction.

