8.2.3. Palm/Sole Assessment

Thickening of the skin on the palms and soles will be measured on a 5-point scale at all clinic visits. The scoring is as follows in [Table 7](#).

Table 7: Palm/Sole Scoring Definitions

Score	Definition
0	Clear: No thickening, no roughness, no fissure
1	Almost clear: Only slight thickening, minimal to no roughness, no fissures
2	Mild: Some thickening, mild roughness on palpation, few fissures may be present
3	Moderate: Substantial and diffuse thickening, coarse roughness on palpation may be present, fissures may be present
4	Severe: Very thickened and rough skin, numerous fissures

The change from baseline palm/sole assessment score will be analyzed using an MMRM. The MMRM model will include change from baseline in palm/sole assessment score as the dependent variable, treatment, study visit, treatment-by-visit interaction, and age group as fixed effects, subject as a random effect, and baseline palm/sole assessment score as a covariate. All post-baseline study visits will be included in the model; however, the primary comparison will be between the active trifarotene cream HE1 groups and vehicle at Day 90. An unstructured covariance matrix will be used to model the within-subject errors. The Kenward-Roger approximation will be used to estimate degrees of freedom. In case of convergence issues, other covariance structures will be explored including AR(1), CS, and VC with each model fit to find the covariance structure with the best fit. The fit statistics will be compared for all covariance structures; the structure with the smallest Akaike information criterion will be retained as the preferred model and noted in the resulting table. For the OLE period, the model will not include treatment or treatment-by-visit interaction since all subjects receive the same treatment in the OLE.

The LS mean change from baseline will be presented along with the associated 95% CI within each treatment group. The overall P value of the model will be presented to test the null hypothesis that the change from baseline to subsequent study visit is 0 with a 2-sided alternative considering a difference in either direction.

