The change from baseline DLQI/cDLQI score will be analyzed using an MMRM. The MMRM model will include change from baseline in DLQI/cDLQI score as the dependent variable, treatment, study visit, and treatment-by-visit interaction as fixed effects, subject as a random effect, and baseline DLQI/cDLQI score as a covariate. All post-baseline study visits will be included in the model; however, the primary comparison will be between the active trifarotene cream HE1 groups and vehicle at Day 90. An unstructured covariance matrix will be used to model the within-subject errors. The Kenward-Roger approximation will be used to estimate degrees of freedom. In case of convergence issues, other covariance structures will be explored including AR(1), CS, and VC with each model fit to find the covariance structure with the best fit. The fit statistics will be compared for all covariance structures; the structure with the smallest Akaike information criterion will be retained as the preferred model and noted in the resulting table.

The LS mean change from baseline will be presented along with the associated 95% CI within each treatment group. The overall *P* value of the model will be presented to test the null hypothesis that the change from baseline to subsequent study visit is 0 with a 2-sided alternative considering a difference in either direction.

In comparing treatments (active trifarotene cream HE1 groups minus vehicle), LS mean differences in change from baseline will be presented along with associated 95% CIs and *P* values. The null hypothesis that the difference in change from baseline in active trifarotene cream HE1 groups minus control vehicle is 0 with a 2-sided alternative considering a difference in either direction.

The observed value and change from baseline in DLQI/cDLQI score will also be summarized descriptively by study visit and treatment group using descriptive statistics in addition to the above noted model for the Double-blind Period.

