Abbreviations: CFB = change from baseline; CI = confidence interval; IGA = Investigator's Global Assessment; ITT = intent to treat; LS = least-squares; MMRM = mixed model for repeated measures; SD = standard deviation; SE = standard error.

Note: Subjects are summarized by randomized treatment group. The 5-point (0 - 4) IGA is a measure of disease severity which considers both scaling and roughness. Higher IGA scores represent more severe disease.

[1] LS mean CFB, LS mean differences (Trifarotene cream HE1 - vehicle), 95% CIs, and P values were obtained from a mixed model for repeated measures (MMRM) with change from baseline in IGA score as the repeated dependent variable, fixed effect terms for baseline IGA score, treatment, study visit, treatment-by-study visit interaction, and age group as independent variables. An unstructured covariance matrix was used to model the within-subject correlation. Age group is defined as adolescents (ages 12 to 17 years, inclusive) and adults ≥18 years.

[2] Baseline is defined as the last non-missing assessment recorded prior to the first dose of treatment in the Double-blind Period.

SOURCE: Listing 16.2.6.1

Programming note: If the unstructured covariance structure does not converge, use other structures as outlined in the SAP section 8.1 and update the footnote accordingly. Include Days 30, 60, and 90 as well. Rows will be the same as what is displayed for Day 14. Repeat Table for Overall Trifarotene cream HE1 and Vehicle columns. Vehicle column will not have Comparison vs. Vehicle row cells populated.

Table 14.2.1.6.2
MMRM Analysis of Change from Baseline in IGA Score
OLE ITT Population

Programming note: Update Note: to read “Subjects are summarized by treatment group. All subjects received Trifarotene cream HE1 200 ug/g in the OLE.”

Only include one set of columns for Trifarotene cream HE1 200 ug/g.

Do not include Comparison vs. Vehicle rows.

Baseline [2], Days 104, 120, 150, 180, and 194 will be displayed.

Update footnote [1] to read “LS mean CFB, 95% CIs, and P values were obtained from a mixed model for repeated measures (MMRM) with change from baseline in IGA score as the repeated dependent variable, fixed effect terms for baseline IGA score, study visit, and age group as independent variables. An unstructured covariance matrix was used to model the within-subject correlation. Age group is defined as adolescents (ages 12 to 17 years, inclusive) and adults ≥ 18 years.”

Table 14.2.7.1.1

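### The MMRMs in SAP 8.1.1 and 8.2.1 to 8.2.4 pair a random subject effect with an unstructured within-subject matrix, leaving one covariance parameter unidentifiable and risking a needless switch to the fallback structures

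*SAP*

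**What the plan says.** Section 8.1.1 gives the IGA change model fixed effects for treatment, visit, their interaction and age group, with "subject as a random effect, and baseline IGA score as a covariate". It then states: "An unstructured covariance matrix will be used to model the within-subject errors". Degrees of freedom are Kenward-Roger. If there are convergence issues, a term the SAP does not define, AR(1), CS and VC are tried and the structure with the smallest AIC is kept. The SAP does not say whether the random subject effect stays under those structures.

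The same random-effect wording recurs in:

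- 8.2.1 (VIIS): "subject as a random effect, and baseline VIIS score as a covariate"
- 8.2.2 (roughness): "subject as a random effect, and baseline individual score for roughness as a covariate"
- 8.2.3 (palm/sole): "subject as a random effect, and baseline palm/sole assessment score as a covariate"
- 8.2.4 (DLQI/cDLQI): "subject as a random effect, and baseline DLQI/cDLQI score as a covariate"

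Each of these sections also asks for an unstructured matrix and has the same fallback. For the OLE, where a model is planned, only treatment and its interaction with visit are dropped.

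The shells in Section 14.2 differ. Footnote [1] of Table 14.2.1.6.1 lists "fixed effect terms for baseline IGA score, treatment, study visit, treatment-by-study visit interaction, and age group as independent variables" together with an unstructured matrix, and names no random effect. The corresponding footnotes for the other MMRM tables follow the same pattern.

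All five text sections also contain this sentence: "The overall *P* value of the model will be presented to test the null hypothesis that the change from baseline" to a later visit is zero.

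**The concern.** A random subject intercept adds the same constant to every element of the subject's covariance matrix. An unstructured residual matrix can already absorb any such constant. The text therefore specifies a model with one parameter too many, and the shells specify a different, identifiable model. Programmers working from Section 8 and from the shells would write different code.

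The fallback rule is what gives this practical weight. A singular Hessian or failed convergence caused only by the surplus term could be taken as a convergence issue. The analysis would then move to a more restrictive covariance structure although nothing was wrong with the unstructured one. This affects IGA change and the four secondary endpoints analysed by MMRM.

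The P value sentence is a smaller, separate error in the same paragraphs. A test of the model as a whole does not test whether the mean change at a given visit is zero.

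**Working it through.** The plan gives no figure to reproduce here. The question is whether the covariance parameters can be estimated.

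**Inputs.** Double-blind post-baseline visits: Days 14, 30, 60 and 90, so T = 4 (Table 14.2.1.6.1 shell). OLE visits: Days 104, 120, 150, 180 and 194, so T = 5 (Table 14.2.1.6.2 shell), assuming that the OLE model uses the visits displayed. Subjects enrolled: 65 (Section 1).

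**Algebra.** Let J be the T × T matrix of ones, σ_b² the subject variance and R the unstructured residual matrix. The marginal covariance is

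V = σ_b² J + R.

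For any constant c, replacing σ_b² by σ_b² + c and R by R − cJ leaves V unchanged. As long as both parts remain valid, the data cannot choose between them.

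**Parameter count.** V has T(T+1)/2 distinct elements and the text's model has T(T+1)/2 + 1 parameters.

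- Double-blind: 4 × 5 / 2 = 10 elements, 10 + 1 = 11 parameters.
- OLE: 5 × 6 / 2 = 15 elements, 15 + 1 = 16 parameters.

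The surplus is exactly one whatever T is. The rank of the derivative of V with respect to its parameters confirms this: 10 for the 11 parameters and 15 for the 16.

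**Fallback structures, if the random effect is kept** (same result for T = 4 and T = 5):

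| Structure for R | Parameters including σ_b² | Rank |
|---|---|---|
| Unstructured, T = 4 | 11 | 10 |
| Unstructured, T = 5 | 16 | 15 |
| CS | 3 | 2 |
| AR(1) | 3 | 3 |
| VC | 2 | 2 |

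CS is redundant for the same reason as unstructured. VC with a random subject is identifiable and equals CS with a non-negative covariance. If the random effect is dropped instead, VC treats a subject's visits as independent.

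**Numerical illustration.** One REML fit was run on simulated data: 65 subjects, three arms, four visits, and about 20% monotone dropout. The data and variances are assumptions.

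- Unstructured R alone: minimised −2 restricted log-likelihood 67.894.
- Random subject effect added, at σ_b² = 0, 0.0605, 0.1210, 0.1814 and 0.2298 with R reduced to match: 67.894 each time. R stays positive definite up to σ_b² = 0.242.
- Hessian in the 11 parameters: one eigenvalue is numerically zero (about 4 × 10⁻⁵) and the others run from 133 to 2766.

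The optimum is a ridge along σ_b², not a point, and removing the random effect costs nothing in fit.

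**P value wording.** Against the overall model test in the text, the Table 14.2.1.6.1 shell shows a P value for zero change from baseline at each visit and in each arm. The shell has the quantity that tests the stated hypothesis.

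**The case against.** The strongest reply is that results do not change. V and the fixed effects remain identifiable, so LS means and their differences are the same if the fit completes. Software may simply set σ_b² to zero and proceed, and no run was shown to fail. The shells suggest that the ordinary MMRM was meant and that the random-effect phrase is loose wording for the subject block. The primary analysis is logistic regression and does not use this model, and Section 6.1.3 makes secondary and exploratory P values informational only. All of this stands. It makes the point a correction of specification. It does not remove it, because text and shells still differ and the fallback trigger is undefined.

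Two stronger readings are tempting and are not supported.

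- **Kenward-Roger degrees of freedom are corrupted.** V is linear in the covariance parameters. Write the 10 elements of V as Aθ, with A of full row rank and I the information for those elements. The information for θ is then A′IA, and A(A′IA)⁻A′ = I⁻¹ for any generalised inverse. The adjustment therefore matches that of the plain unstructured model unless the software fails on the singular matrix. No degrees of freedom were computed that show otherwise.
- **The AIC comparison is wrong throughout.** With the random effect kept, AR(1) and VC have as many identifiable parameters as are counted. Only unstructured and CS carry a surplus parameter.

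**Conclusion.** The point holds as a defect of specification. Five sections describe a model with exactly one unidentifiable covariance parameter: 11 for 10 in the double-blind period, and 16 for 15 in the OLE for IGA, VIIS, roughness and palm/sole. This follows from algebra and does not rest on the simulation. The OLE count assumes five visits in the model.

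The consequence is a risk: a singular-Hessian or convergence failure that needlessly triggers the fallback. How often that would happen depends on the software and was not measured. A reader might infer that treatment estimates are biased or that every continuous secondary measure is affected. Neither follows. Estimates are unaffected when the fit completes, and the number of fissures is only summarised descriptively (8.2.5). The primary analysis is untouched.

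The text should be corrected because it conflicts with the plan's own shells. The P value sentence should be corrected with it.

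**What to change.** 1. In 8.1.1 and 8.2.1 to 8.2.4, delete the random-subject term. State that subject only defines the repeated-measures block and that unstructured R is the primary structure, as in the shells.
2. For the fallback, specify AR(1) or CS for R without a random subject effect. Remove VC, or define it as a random subject intercept with independent residuals, which is CS with non-negative covariance. Then no candidate is redundant and none assumes independent visits. Deleting the random effect while leaving VC as it is would create that independence assumption.
3. In the same sections, replace the overall model P value with the P value for the LS mean change from baseline at each visit, as in the Table 14.2.1.6.1 shell.

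After the change, the unstructured model has 10 parameters at rank 10 (double-blind) and 15 at rank 15 (OLE). The cost is wording in five sections, best settled before unblinding. It needs no new data and no extra analysis, and the shell footnotes for the primary structure can stay as they are.

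### The only fallback covariance structures named for the MMRMs assume equal variance at every visit, so the Day 90 standard error is misstated if the unstructured fit fails and variability changes over time

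*SAP*

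**What the plan says.** For change in IGA, Section 8.1.1 starts from the most general choice: "An unstructured covariance matrix will be used to model the within-subject errors". It also puts subject in the model as a random effect. If convergence fails, it turns to AR(1), "compound symmetry (CS), and variance components (VC) with each model fit to find the covariance structure with the best fit". The selection rule is that "the structure with the smallest Akaike information criterion will be retained as the preferred model and noted in the resulting table". The target is narrow: "the primary comparison will be between the active trifarotene cream HE1 groups and vehicle at Day 90". On small-sample inference, "The Kenward-Roger approximation will be used to estimate degrees of freedom"; no empirical (sandwich) standard error is planned.

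The same fallback text recurs for VIIS in Section 8.2.1 ("other covariance structures will be explored including AR(1), CS, and VC"), roughness in 8.2.2, palm/sole in 8.2.3 and DLQI/cDLQI in 8.2.4. The programming note to the shell of Table 14.2.1.6.1 only points back to Section 8.1. No structure with visit-specific variances, other than the unstructured one, is named anywhere in the SAP.

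**The concern.** The unstructured matrix lets each visit have its own variance. Each named replacement removes exactly that feature. AR(1) and CS have a constant diagonal, and VC errors are a constant times the identity. The random subject effect adds the same constant to every element, so the diagonal stays constant. Random effect plus VC is marginally the same form as CS.

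AIC can rank the three but cannot repair a restriction they share. Kenward-Roger corrects for estimating the covariance parameters, not for a wrong covariance form. The Day 90 standard error is then built from a variance pooled over all visits.

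Rising variance is plausible for IGA. Subjects enter at grade 3 or 4, so early changes cluster near zero, while the planning rates in Section 3 are 40% and 70% success with at least a 2-grade change. As an illustration, treat change as two-valued, with 40% responders at Day 90 and an assumed 5% to 10% at Day 14. The Day 14 to Day 90 SD ratio is then sqrt(0.0475/0.24) = 0.44 to sqrt(0.09/0.24) = 0.61.

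These MMRMs carry four of the five secondary endpoints listed in Section 2.2.2.2. Their Day 90 intervals and P values would be too optimistic if the fallback were used and variance had risen.

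**Working it through.** **Inputs from the SAP.** 65 subjects enrolled (Section 1), randomised 1:1:1, so 65/3, about 22 per arm; four post-baseline double-blind visits (Days 14, 30, 60, 90); two-sided 0.05 (Section 4.1); 20% dropout planned (Section 4.2). The SAP states no SD, standard error or power for any MMRM, so there is no figure of its own to reproduce. The visit SDs and the correlation below are assumptions.

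**Analytic check.** With complete data and separate means by arm and visit, the Day 90 contrast is the difference in Day 90 arm means. Its true variance is SD90² × (1/n1 + 1/n2). CS and VC replace SD90² by the mean of the four visit variances. Hence:

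- r = model SE / true SE = sqrt(mean of visit variances / Day 90 variance)
- actual type I error ≈ 2 × (1 − Φ(1.96 × r))

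For example, 0.60/0.75/0.90/1 gives (0.36 + 0.5625 + 0.81 + 1)/4 = 0.6831, r = 0.827, 1.96r = 1.62, error 10.5%.

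| SDs at Days 14/30/60/90 | Mean variance / Day 90 variance | r | Type I error |
|---|---|---|---|
| 1/1/1/1 | 1.0000 | 1.000 | 5.0% |
| 0.80/0.87/0.94/1 | 0.8201 | 0.906 | 7.6% |
| 0.60/0.75/0.90/1 | 0.6831 | 0.827 | 10.5% |
| 0.50/0.70/0.85/1 | 0.6156 | 0.785 | 12.4% |
| 1/0.9/0.8/0.7 | 0.735/0.49 = 1.5000 | 1.225 | 1.6% |

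**Simulation of the pooled variance.** 8,000 null trials per scenario, arms of 22/22/21, correlation 0.6: 7.0%, 10.0% and 12.0% for the three widening scenarios. Using the Day 90 variance alone gave 4.7% to 5.2%.

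**Simulation of the planned rule.** REML fits of CS, AR(1) and VC with smallest-AIC choice; 22/22/21 subjects, AR(1) correlation 0.6, 20% monotone dropout, 800 runs (Monte Carlo error about 1 percentage point). A t reference with 62 df stood in for Kenward-Roger, and there was no baseline or age covariate and no random subject effect.

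| SDs | SE ratio, AIC choice | Type I error, AIC choice |
|---|---|---|
| 1/1/1/1 | 1.013 | 4.0% |
| 0.60/0.75/0.90/1 | 0.793 | 12.0% |
| 0.50/0.70/0.85/1 | 0.771 | 13.4% |
| 1/0.9/0.8/0.7 | 1.252 | 1.2% |

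Without dropout, 0.50/0.70/0.85/1 gave 10.9%. CS, AR(1) and VC taken singly behaved alike, so the choice among them hardly matters.

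**Check of the remedy.** In a further 500 null trials per scenario (same arms, correlation and dropout; t with 55 df; Monte Carlo error 1 to 1.5 points), AIC choice between AR(1) and CS gave 7.2%, 9.6% and 11.6% in the three widening scenarios and 5.6% with equal SDs. ARH(1) and CSH each gave 5.2% throughout. The scenarios shared a seed, and these fits are unaffected by rescaling a visit, so the identical 5.2% is in effect one experiment. Heterogeneous Toeplitz was not simulated.

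**Why the unstructured fit may fail.** Four visits give 4 × 5/2 = 10 distinct variances and covariances, and the unstructured matrix already uses 10 parameters. A random subject variance makes 11 parameters for 10 quantities, so it cannot be identified separately.

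**The case against.** The case for leaving the text alone has real content.

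- *The list is open.* The SAP says structures including these three will be explored. A reader might infer that every permitted fallback forces equal variances. The text does not support that: a heterogeneous structure is not forbidden, only not named or ordered.
- *VC.* A reader might infer that VC treats a subject's visits as independent. With the random subject effect in the same model it does not; only the equal-variance restriction remains.
- *Two conditions must both hold.* The unstructured fit must fail, and variance must change over visits. With 20% dropout about 0.8 × 65 = 52 subjects would complete, which may well support 10 covariance parameters once the redundant random effect is removed. No convergence check has been made. The cDLQI model, fitted separately in Table 14.2.5.2 on subjects using the children's version, is the most exposed, but its size is not given.
- *The widening argument is specific to scale.* It is made for IGA and carries over less surely to VIIS totals (0 to 16) or DLQI/cDLQI (0 to 30).
- *Limited consequence.* Section 6.1.3 calls secondary and exploratory P values informational, the chosen structure is to be noted in the table, and by-visit SDs are tabulated, so widening would be visible.

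These points limit the reach and size of the problem. They do not remove it: every structure the SAP actually names shares the restriction, and the stated selection rule cannot correct it.

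**Conclusion.** The point holds as a conditional weakness in the fallback rule. If the unstructured fit fails, one of the named structures is used and change scores widen over time, the Day 90 standard error is too small. Under the assumed SD ratios a nominal 5% test then runs at about 7% to 12%, slightly more in the runs with 20% dropout. If variability falls over time the error is in the conservative direction, about 1.6% in the case computed; with equal variances there is no problem. The size rests wholly on assumed SDs, since the SAP gives none.

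It would be wrong to infer that the primary result is at risk: treatment success is analysed by logistic regression. What is affected is the supporting analysis of IGA change and the secondary MMRMs. The SAP describes itself as set before unblinding, so the rule is best settled there and not when a model fails.

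**What to change.** In Sections 8.1.1 and 8.2.1 to 8.2.4:

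1. Drop the separate random subject effect whenever an unstructured or other full within-subject error matrix is used. The model footnote of Table 14.2.1.6.1 already lists no such effect.
2. Replace the AIC choice by a fixed order of structures with visit-specific variances: heterogeneous Toeplitz, then ARH(1), then CSH. Use the first that converges.
3. Keep a homogeneous structure such as CS only as the last resort, so that an analysis is still defined if all three fail, and report it with an empirical (sandwich) standard error. Name the degrees-of-freedom rule for that step, because Kenward-Roger adjusts the model-based covariance.

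The cost is SAP wording and, in the fallback case only, a little precision. At four visits heterogeneous Toeplitz has 7 covariance parameters (4 variances and 3 correlations) against 2 for CS or AR(1), five more. ARH(1) and CSH have 5 each, three more.
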